11.2	Responsibilities of the investigator and IRB	35
12	Protocol adherence	36
12.1	Protocol Amendments	36
13	References	37

List of abbreviations

AE	adverse event
AESI	adverse event of special interest
ALP	alkaline phosphatase
ALT	alanine aminotransferase
ARDS	acute respiratory distress syndrome
AST	aspartate aminotransferase
BMI	Body Mass Index
BUN	blood urea nitrogen
CDS	Core Data Sheet (for marketed drugs)
CFR	Code of Federal Regulation
CK	Creatinine kinase
CK-MB	Creatinine kinase MB
COAR	Clinical Operations, Analytics & Regions
COVID-19	coronavirus disease 2019
CRF	Case Report/Record Form (paper or electronic)
CRO	Contract Research Organization
CRP	C-reactive protein
CTC	Common Toxicity Criteria
CTRDB	Clinical Trial Results Database
CV	coefficient of variation
DMC	Data Monitoring Committee
EC	Ethics committee
Echo	Echocardiogram
ECG	Electrocardiogram
EDC	Electronic Data Capture
ELISA	Enzyme-linked immunosorbent assay
eSAE	Electronic Serious Adverse Event
FDA	Food and Drug Administration
GCP	Good Clinical Practice
GM-CSF	Granulocyte-macrophage colony stimulating factor
h	hour
HIV	human immunodeficiency virus
IL-6	Interleukin-6
i.v.	intravenous
ICH	International Conference on Harmonization of Technical Requirements for Registration of Pharmaceuticals for Human Use
IEC	Independent Ethics Committee
IRB	Institutional Review Board
IRT	Interactive Response Technology
LDH	lactate dehydrogenase
LFT	Liver function test

LLN	lower limit of normal
LLQ	lower limit of quantification
MABEL	minimum anticipated biological effect level
MedDRA	Medical dictionary for regulatory activities
MODS	multiple organ dysfunction syndromes
mg	milligram(s)
MI	myocardial infarction
mL	milliliter(s)
ml	milliliter(s)
MRSD	maximum recommended starting dose
o.d.	once a day
p.o.	oral
PD	pharmacodynamic(s)
PK	pharmacokinetic(s)
RBC	red blood cell(s)
RDC	Remote Data Capture
REB	Research Ethics Board
s.c.	subcutaneous
SAE	serious adverse event
SARS-CoV2	severe acute respiratory syndrome coronavirus 2
sCR	serum creatinine
SD	standard deviation
SGOT	serum glutamic oxaloacetic transaminase
SGPT	serum glutamic pyruvic transaminase
SOM	Site Operations Manual
SUSAR	Suspected Unexpected Serious Adverse Reactions
TB	tuberculosis
TBL	total bilirubin
TNF- α	Tumor necrosis factor alpha
ULN	upper limit of normal
ULQ	upper limit of quantification
WBC	white blood cell(s)
WHO	World Health Organization

1 Introduction

1.1 Background

The 2019 novel coronavirus (2019-nCoV; severe acute respiratory syndrome coronavirus 2 (SARS-CoV-2)) has spread rapidly since its recent identification in patients with severe pneumonia in Wuhan, China and resulted in a worldwide pandemic (COVID-19). Given the burden of disease, effective treatments are urgently required.

The 2019-nCoV has affinity for cells in the lower respiratory tract and can replicate there, causing radiological evidence of lower respiratory tract lesions in patients who do not present with clinical pneumonia. There seem to be three major patterns of the clinical course of infection: mild illness with upper respiratory tract presenting symptoms; non-life-threatening pneumonia; and severe pneumonia with acute respiratory distress syndrome (ARDS) that begins with mild symptoms for 7–8 days and then progresses to rapid deterioration and ARDS requiring advanced life support.

In clinical and epidemiological data from the Chinese CDC regarding 72,314 case records, providing an important illustration of the epidemiologic curve of the Chinese outbreak, the overall case-fatality rate (on confirmed cases) was 2.3%. Of note, the fatal cases were primarily elderly patients, in particular those aged ≥ 80 years (about 15%) and 70 to 79 years (8.0%). Approximately half (49.0%) of the critical patients were affected by preexisting comorbidities such as cardiovascular disease, diabetes, chronic respiratory disease, and oncological diseases died.

In one of the first reports on the disease, Huang et al. illustrated that patients ($n = 41$) suffered from fever, malaise, dry cough, and dyspnea. Chest computerized tomography (CT) scans showed pneumonia with abnormal findings in all cases. The clinical spectrum of COVID-19 varies from asymptomatic or pauci-symptomatic forms to clinical conditions characterized by respiratory failure that necessitates mechanical ventilation and support in an intensive care unit (ICU), to multi-organ and systemic manifestations in terms of sepsis, septic shock, and multiple organ dysfunction syndromes (MODS). In an initial report, about a third of patients required ICU care and 15% of cases were fatal. Similarly, in a more recent report of 201 hospitalized patient, 41.8% developed acute respiratory distress syndrome (ARDS), and 52.4% of these patients die.

In Italy, the case-fatality rate has been reported at 7.2%. Furthermore, in an initial US experience of 21 critically ill patients, 11 had died at the time of publication, and only 2 survived transfer out of the ICU, highlighting the need for effective treatments before patients become critically ill.

Among the severe clinical manifestations, there are severe pneumonia and ARDS. Although the clinical course of the disease seems to predict a favorable trend in the majority of patients; in a percentage of cases still to be defined, after about a week, there is a sudden worsening of clinical conditions with rapidly worsening respiratory failure and MOD/MOF. Criteria for definition of specific subpopulations are defined:

- *Severe Pneumonia.* Fever is associated with severe dyspnea, respiratory distress, tachypnea (> 30 breaths/min), and hypoxia ($\text{SpO}_2 < 90\%$ on room air). However, the fever symptom must be interpreted carefully as even in severe forms of the disease, it can be moderate or even absent.
- *Acute Respiratory Distress Syndrome (ARDS).* The diagnosis requires clinical and ventilatory criteria. This syndrome is suggestive of a serious new-onset respiratory failure or of worsening of an already-identified respiratory picture. Different forms of ARDS are distinguished based on the degree of hypoxia. The reference parameter is the $\text{PaO}_2/\text{FiO}_2$: a ratio ≤ 315 is suggestive of ARDS.
 - Mild ARDS: $200 \text{ mmHg} < \text{PaO}_2/\text{FiO}_2 \leq 300 \text{ mmHg}$. In non-ventilated patients or in those managed through non-invasive ventilation (NIV) by using positive end-expiratory pressure (PEEP) or a continuous positive airway pressure (CPAP) $\geq 5 \text{ cmH}_2\text{O}$.
 - Moderate ARDS: $100 \text{ mmHg} < \text{PaO}_2/\text{FiO}_2 \leq 200 \text{ mmHg}$.
 - Severe ARDS: $\text{PaO}_2/\text{FiO}_2 \leq 100 \text{ mmHg}$.

Unfortunately, no drug or vaccine has yet been approved to treat human coronaviruses. Several options can be envisaged to control or prevent emerging infections of 2019-nCoV, including vaccines, monoclonal antibodies, oligonucleotide-based therapies, peptides, interferon and small-molecule therapies. Although the potential repurposing of existing antiviral agents to treat COVID-19 is already moving into clinical trials, new interventions based on drugs directly active on the virus itself are likely to require months to years to develop.

Accumulating evidence suggests that a subgroup of patients with severe COVID-19 might have a cytokine storm syndrome, leading to pneumonia, respiratory failure, need for mechanical ventilation, and often death. The identification of hyper-inflammation and treatment using existing therapies that are either in clinical development or approved in other indications with understood safety profiles is a relevant option to address the immediate need to reduce the rising mortality and need for ventilatory support.

In light of pathological findings of pulmonary edema and hyaline membrane formation, timely and appropriate use of drugs aimed at reducing inflammation in a targeted way, together with ventilator support, should be considered for patients with hyper-inflammation to prevent and treat ARDS development. A cytokine profile resembling secondary hemophagocytic lymphohistiocytosis (sHLH) is associated with COVID-19 disease severity, characterized by increased interleukin (IL)-2, IL-7, granulocyte-colony stimulating factor, interferon- γ inducible protein 10, monocyte chemoattractant protein 1, macrophage inflammatory protein 1- α , and tumor necrosis factor- α . Predictors of fatality from a recent retrospective, multicenter study of 150 confirmed COVID-19 cases in Wuhan, China, included elevated ferritin (mean 1297.6 ng/ml in non-survivors vs 614.0 ng.ml in survivors; $p<0.001$) and IL-6 ($p<0.0001$) suggesting that mortality might be due to a dysfunctional hyper-inflammatory response while clearing the virus (i.e. a hyperinflammatory state driven by the host, not the virus).

In hyper-inflammation, immunosuppression is likely to be beneficial. In fact, in a subgroup analysis of a randomized controlled trial, patients with sepsis and organ dysfunction or hyper-inflammation had improved survival with IL-1 receptor antagonism, and this therapy has not been associated with adverse events, even at high doses. A multicenter, randomized controlled trial of tocilizumab (IL-6 receptor blockade, licensed for cytokine release syndrome), has been approved in China in patients with COVID-19 pneumonia and elevated IL-6 (ChiCTR2000029765).

In our study, we aim to enroll patients with severe COVID-19 pneumonia and hyper-inflammation to identify the subgroup of patients for whom immunosuppression could prevent worsening of pulmonary status, including the need for ventilatory support, with the aim ultimately to improve mortality.

Rationale for mavrilimumab

GM-CSF strongly activates macrophages and is considered to be a pro-inflammatory cytokine. GM-CSF production is associated with tissue inflammation. GM-CSF-derived signals are critically involved in the differentiation of macrophages and in the proliferation and activation of other immune cells. GM-CSF-activated macrophages produce pro-inflammatory cytokines, including tumor necrosis factor (TNF), IL-1 β , IL-6, IL-23 and IL-12. In addition, GM-CSF receptor activation triggers stimulation of multiple downstream signaling pathways, including Janus kinase 2 (JAK2)/signal transducer and activator of transcription 5 (STAT5), the mitogen-activated protein kinase (MAPK) pathway, and the phosphoinositide 3 kinase (PI3K) pathway, all relevant in activation and differentiation of myeloid cells.

Under physiologic conditions, levels of circulating GM-CSF are low, but levels are elevated in inflammatory conditions. Several cell types can serve as a source of GM-CSF, including fibroblasts, endothelial cells, macrophages, dendritic cells, T cells, neutrophils, eosinophils, and cancer cells, with most production occurring locally at the site of inflammation. This in turn exacerbates the inflammatory reaction via cytokine pathways that have been termed the colony stimulating factor network. GM-CSF can be induced by inflammatory cytokines and in turn increases production of pro-inflammatory cytokines, thus functioning as a feed-forward inflammatory amplifier.

Zhou et al (2020) recently reported elevated levels of GM-CSF in the lungs of patients with COVID-19, specifically showing that, after the 2019-nCoV infection, CD4+T lymphocytes are rapidly activated to become pathogenic T helper (Th) 1 cells and generate GM-CSF, etc. The cytokine environment induces inflammatory CD14+CD16+ monocytes with high expression of IL-6 and accelerates the inflammation. The authors further contend that these aberrant and excessive immune cells may enter the pulmonary circulation in huge numbers and play an immune-mediated damaging role, causing lung dysfunction and rapid mortality.

GM-CSF signals through GM-CSF-R, which consists of a specific ligand-binding α -chain (GM-CSF-R α) and a signal-transducing β -chain (GM-CSF-R β) that is common to IL-3 and IL-5 receptors. Hence, GM-CSF-R signaling can be specifically targeted with antibodies

directed at GM-CSF-R α . Mavrilimumab is an anti-GM CSF-R α monoclonal antibody (human isoform IgG4) previously developed by MedImmune and now in development by Kiniksa Pharmaceuticals that has been shown to inhibit the GM-CSF signaling axis in humans and improve clinical outcomes measures in a Phase 2 program in Rheumatoid Arthritis.

1.2 Purpose

The purpose of this prospective, proof-of-concept Phase 2, multicenter, blinded, randomized placebo controlled study is to demonstrate that early treatment with mavrilimumab prevents progression of respiratory failure in patients with severe COVID-19 pneumonia and clinical and biological features of hyper-inflammation. These results will lead to and inform a Phase III randomized placebo-controlled trial.

2 Objectives and endpoints

Primary Objective

To demonstrate that early treatment with mavrilimumab prevents progression of respiratory failure in patients with severe COVID-19 pneumonia and clinical and biological features of hyper-inflammation.

Secondary Objectives

- To evaluate mortality
- To evaluate the duration of hospitalization
- To evaluate safety of mavrilimumab

Primary Endpoint

The primary endpoint is the proportion of subjects alive and off of oxygen at day 14.

When hospitalized patients are off of oxygen, this will be documented as an oxygen saturation >90% for at least 5 minutes at rest. For patients that are discharged before day 14, a telehealth visit will be performed at day 14. For patients discharged **off** of oxygen before day 14, the day 14 visit will assess that they are off of oxygen. For patients who are discharged **on** oxygen before day 14, the decision to discontinue oxygen will be based on standard clinical care according to the health provider who prescribed oxygen therapy. The day 14 telehealth visit will assess whether the patient remains on oxygen, and “off of oxygen” will be defined as no supplemental oxygen use for at least the previous 24 hours.

Secondary Endpoints

The secondary end-points are alive at day 28, and the proportion of subjects alive and without respiratory failure at 28 days. Respiratory failure is defined as needing mechanical ventilation, non-invasive ventilation, or high-flow oxygen.

Exploratory Endpoints

- Mortality at day 14
- Mortality at day 60
- Proportion of patients in each category according to the following ordinal scale at day 7, 14, 21, and 28:
 1. Not hospitalized
 2. Hospitalized, no supplemental oxygen
 3. Hospitalized, on supplemental oxygen
 4. Hospitalized, requiring nasal high-flow oxygen or non-invasive ventilation
 5. Hospitalized, requiring ECMO, invasive mechanical ventilation or both
 6. Death
- Freedom from mechanical ventilation
- Duration of hospitalization
- Change in SOFA score at day 7, day 14, day 21, and day 28, or until discharge
- Reduction in CRP at day 7 and day 14 (understanding that labs may be obtained until patient discharge)
- Time to negative SARS-CoV2 RNA levels in oropharyngeal or nasopharyngeal swabs
- Worst value for PaO₂/FiO₂ (or SaO₂/FiO₂ if PaO₂ not available) at day 3, day 5, day 7, day 14, day 21 and day 28, or until discharge
- Safety including number of adverse events and serious adverse events

3 Study design

This prospective, proof-of-concept Phase 2, multi-center, blinded randomized placebo-controlled study is designed to demonstrate that early treatment with mavrilimumab prevents progression of respiratory failure in patients with severe COVID-19 pneumonia and clinical and biological features of hyper-inflammation while gathering data to support a larger Phase III randomized controlled trial.

The study population includes patients who meet criteria of impending mechanical ventilation.

Enrollment: The study will be performed in approximately 4 months total, starting from the first patient enrolled with enrollment expected to complete within 2 months.

Follow-up period: The follow-up period is 60 days for each patient enrolled.

A total of 60 patients will be randomized using a 1:1 allocation ratio: 30 subjects will receive mavrilimumab at 6mg/kg IV, and 30 subjects will receive placebo infusion. The investigator, clinical team, and subject will be blinded to treatment assignment.

Participants will be identified by regular review of hospitalized COVID19 patients to evaluate for inclusion and exclusion criteria. Participants will then be approached in the standard manner by study investigator and coordinator/research nurse.

Research interventions will take place in the hospital in accordance with privacy standards.

The study team is informed on all study procedures and requirements with daily meetings and the opportunity to continuously update through secure channels.

In this multicenter consortium, each participating site will have their own IND for patients enrolled at their site. However, data collection, data analysis, and randomization scheme will be performed at one site, Cleveland Clinic C5 Research.

4 Rationale

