5.1 Inclusion criteria

The eligibility criteria, including the inclusion and exclusion criteria, will be verified both by a study investigator and a research nurse using checklists.

Subjects eligible for inclusion in this study must meet **all** of the following criteria:

1. Written informed consent must be obtained before any assessment is performed
2. Documented COVID19 pneumonia defined as positive SARS-CoV2 test **AND** abnormalities/ infiltrates on chest x-ray or computed tomography **AND** active fever or documented fever within 24-48 hours or ongoing anti-pyretic use to suppress fever
3. Hypoxia (Room air SpO₂ <92% or requirement for supplemental oxygen)
4. Increased serum inflammatory marker (CRP > 5 mg/dL)
5. Severity of disease warrants inpatient hospitalization

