5.2 Exclusion criteria

Subjects meeting any of the following criteria are not eligible for inclusion in this study:

1. Onset of COVID-19 symptoms >14 days
2. Age < 18 years-old
3. Hospitalized >7 days
4. Mechanically ventilated
5. Serious concomitant illness which in the opinion of the investigator precludes the patient from enrolling in the trial, including (but not limited to):
 - History of immunodeficiency (congenital or acquired)
 - Neutropenia (absolute neutrophil count <1,500/mm³)
 - History of solid-organ or bone marrow transplant
 - History of current systemic autoimmune or autoinflammatory disease(s) requiring systemic immune-modulating drugs
 - History of myeloproliferative disorder or active malignancy receiving cytotoxic chemotherapy
 - Pre-existing severe pulmonary disease (i.e. steroid dependent asthma, COPD on home oxygen, or other restrictive/obstructive lung disease requiring home oxygen)
 - Pre-existing severe left ventricular systolic dysfunction (i.e. LVEF <35%)
 - Known or suspected active tuberculosis (TB), latent TB, or history of incompletely treated TB or at high risk for latent TB (from exposure or prior incarceration)
 - History of active or latent viral hepatitis (i.e. Hepatitis B or C)
 - Concomitant uncontrolled systemic bacterial or fungal infection
 - Concomitant viral infection other than COVID-19 (e.g. Influenza, other respiratory viruses)
 - History of chronic liver disease with portal hypertension
 - History of end-stage renal disease on chronic renal replacement therapy
6. Recent treatment with cell-depleting biological therapies (e.g., anti-CD20) within 12 months, cell-depleting biological therapies (such as anti-tumor necrosis factor [TNF], anakinra, anti-Interleukin [IL]-6 receptor [e.g. tocilizumab], or abatacept) within 8 weeks (or 5 half-lives, whichever is longer), treatment with alkylating agents within 12 weeks, treatment with cyclosporine A, azathioprine, cyclophosphamide, or mycophenolate mofetil (MMF) within 4 weeks
7. Recent treatment with intramuscular live (attenuated) vaccine within 4 weeks
8. Chronic or recent corticosteroid use > 10 mg/day
9. Pregnant and breast-feeding women
10. Enrolled in another investigational study using immunosuppressive therapy
11. Known hypersensitivity to mavrilimumab or any of its excipients

12. In the opinion of the investigator, unable to comply with the requirements to participate in the study

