10.3 Analysis of the primary and secondary endpoints

Based on preliminary case-control data of patients with severe COVID-19 pneumonia treated with mavrilimumab, we estimate that 40% of patients in the placebo group will meet the primary endpoint compared to 80% of treated patients. A sample size of 30 patients per arm (60 total) will provide at least 80% power to detect this difference using a 2-sided alpha of 0.05.

The results of our study will inform treatment effect to aid in the planning of larger studies. The primary efficacy analysis will be on an intention-to-treat basis and include all patients who are randomized. Use of supplemental oxygen and vital status will be assessed daily up to day 14. Patients will be considered to have met the primary endpoint if the patient is alive at day 14 and has not used supplemental oxygen for at least 24 hours, regardless of whether or not the patient is still in the hospital (i.e. success=1). All other patients will be counted as not meeting the primary endpoint (i.e. success=0), including deaths on or before day 14 and patients for whom information cannot be ascertained (eg.lost to follow-up, withdrew consent, or otherwise missing information on the primary endpoint at day 14). This is analogous to imputing the worst case scenario for missing data.

The primary analysis will report the number and percentage of patients meeting the primary endpoint. The chi-square statistic will be used to test the difference between the two treatment groups. The time to freedom from supplemental oxygen will also be displayed geographically with a Kaplan Meier curve. A two-sided p value of < 0.049 will be considered statistically significant for the primary endpoint, though as noted, an important aspect of this study is to better define the magnitude of the treatment effect of our clinical outcomes to appropriately power larger studies.

The secondary endpoints are the proportion of patients alive at day 28 (i.e. success=1), and the proportion of patients alive and without respiratory failure at day 28 (i.e. success=1). Similar to the primary analysis, patients not meeting the this criteria in each of the secondary endpoints will be considered a failure (i.e. success=0), including deaths on or before day 28 and patients

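### Patients already on high-flow oxygen or non-invasive ventilation can enrol, so the Day-28 respiratory-failure endpoint pools recovery with avoidance of failure; analyse it by baseline support

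*Combined protocol and SAP*

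**What the plan says.** **Definition and endpoint.** Section 2 (Secondary Endpoints) states: "Respiratory failure is defined as needing mechanical ventilation, non-invasive ventilation, or high-flow oxygen". The endpoint built on it is "the proportion of subjects alive and without respiratory failure at 28 days".

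**Entry.** Section 5.1, inclusion 3, requires low room-air saturation "or requirement for supplemental oxygen", with no ceiling on the type or amount of support. In Section 5.2 the only exclusion on current respiratory support is criterion 4, "Mechanically ventilated". The other lung exclusion concerns chronic disease that predates COVID-19.

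**Ordinal scale.** Section 2 gives high-flow oxygen and non-invasive ventilation their own category 4, "Hospitalized, requiring nasal high-flow oxygen or non-invasive ventilation", separate from invasive ventilation in category 5. Table 7-1 collects the scale at screening and on Day 0.

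**Analysis.** Section 10.3 analyses "the proportion of patients alive and without respiratory failure at day 28" as a success/failure proportion, reported as a point estimate with a 95% confidence interval and without multiplicity adjustment. It adds Kaplan-Meier estimates for the secondary endpoint. It specifies no adjustment or breakdown by baseline support. Section 6.2.4 stratifies randomization by site only.

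**Purpose.** Section 1.2 gives the aim as "to demonstrate that early treatment with mavrilimumab prevents progression of respiratory failure in patients with severe COVID-19 pneumonia".

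**The concern.** The endpoint is a status on one day. For a patient who enters on low-flow oxygen, success can mean that failure never occurred. For a patient who enters on high-flow oxygen or non-invasive ventilation, success can only mean coming off that support. One pooled proportion per arm cannot show how much of a difference is recovery and how much is avoidance of failure.

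The trial is meant to supply effect sizes for a larger study, and this is the only primary or secondary endpoint that uses the respiratory-failure definition. A planner reading the pooled estimate would not know which kind of benefit to design for. If baseline support strongly predicts the Day-28 result, ignoring it also gives away some precision in a trial of 60.

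The Kaplan-Meier display has its own gap. If the curve runs to first failure, patients on high-flow oxygen or non-invasive ventilation at entry have had the event at time zero. If it runs to success, the other patients are the ones already there. Section 10.3 does not say which is meant or how either group is handled.

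**Working it through.** **1. Text check.** By Section 2, respiratory failure is any of mechanical ventilation, non-invasive ventilation or high-flow oxygen. Exclusion 4 removes the first. Inclusion 3 accepts any oxygen requirement. The other two states are therefore admissible at entry. Reading exclusion 4 to cover non-invasive ventilation would conflict with Section 2, which lists the two separately, and high-flow oxygen would still be admissible.

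**2. The plan's own figure.** Section 10.3 states power only for the primary endpoint: 40% vs 80%, 30 per arm, two-sided 0.05, at least 80%. With a pooled proportion of 0.60:

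z = [0.40 − 1.96 × √(2 × 0.60 × 0.40/30)] / √[(0.40 × 0.60 + 0.80 × 0.20)/30] = (0.400 − 0.248)/0.1155 = 1.32, so power is about 91%.

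The statement holds. It has no bearing on the Day-28 endpoint, for which the plan gives no rate or power.

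**3. Effect on precision (assumed inputs).** Let f be the share entering in failure, and let success be 90% without and 50% with failure at entry, the same in both arms, with n = 30 per arm. None of these rates is in the documents.

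At f = 0.30:
- Overall success: 0.7 × 0.90 + 0.3 × 0.50 = 0.78.
- Crude variance per patient: 0.78 × 0.22 = 0.1716. SE of the difference: √(2 × 0.1716/30) = 0.107. 95% half-width: 21.0 points.
- Within-stratum variance: 0.7 × 0.09 + 0.3 × 0.25 = 0.138. SE: √(2 × 0.138/30) = 0.096. 95% half-width: 18.8 points.
- Ratio: 0.138/0.1716 = 0.80, a reduction of about 20%.

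Varying the entry share and the outcome gap:

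| Entry share | 90% vs 50%: variance ratio | Half-width, crude to stratified | 90% vs 70%: variance ratio | Half-width, crude to stratified |
|---|---|---|---|---|
| 10% | 0.88 | 17.6 to 16.5 | 0.97 | 16.5 to 16.2 |
| 20% | 0.83 | 19.4 to 17.7 | 0.95 | 17.6 to 17.1 |
| 30% | 0.80 | 21.0 to 18.8 | 0.94 | 18.6 to 18.0 |
| 40% | 0.80 | 22.2 to 19.9 | 0.93 | 19.4 to 18.8 |

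These are large-sample approximations that ignore site stratification.

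**4. Chance imbalance is the same quantity.** At f = 0.30 the SD of the between-arm difference in entry share is √(2 × 0.3 × 0.7/30) = 11.8 points. Multiplied by the 40-point gap, it shifts the crude difference by 4.7 points. As a share of the crude variance, 4.7²/10.7² is about 0.19 (0.196 unrounded, which is 1 − 0.804). This is the reduction found in step 3, so it must not be counted twice. With a 20-point gap the shift is 2.4 points.

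**5. How the pooled difference could split (assumed inputs).** Suppose treatment moves success from 85% to 95% without failure at entry and from 50% to 70% with it. The recovery share of the difference is f × 0.20/[f × 0.20 + (1 − f) × 0.10]: 18%, 33%, 46% and 67% at f = 10%, 20%, 30% and 50%.

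**6. What each stratum can carry.** At f = 0.30 the stratum in failure at entry has 0.3 × 30 = 9 per arm. At 50% success its 95% half-width is 1.96 × √(2 × 0.25/9) = 46 points. At f = 0.10 it has 3 per arm. The other stratum, at f = 0.30 and 90% success, has about 21 × 0.10 = 2 failures per arm.

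**The case against.** Four points on the other side stand.

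- **Purpose.** It concerns progression of respiratory failure, and Sections 3 and 5 describe patients close to needing mechanical ventilation. Enrolling people already on high-flow oxygen or non-invasive ventilation fits that. A reader might infer that eligibility contradicts the objective; the wording does not support this.
- **Validity.** A Day-28 status is a coherent endpoint, and coming off high-flow oxygen is a real benefit. Randomization balances baseline support in expectation. A reader might infer that the comparison is biased, or that chance imbalance is error on top of the planned interval. Neither follows: step 4 shows that the interval already contains the imbalance.
- **Other endpoints.** The exploratory list includes freedom from mechanical ventilation, which no eligible patient has lost at entry, and the full ordinal distribution at Days 7, 14, 21 and 28. Both speak to progression, although neither is planned by baseline category.
- **Status.** Section 10.3 already warns that the secondary intervals are not definitive. The primary endpoint does not use this definition.

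These points limit the weight of the concern. They do not tell a reader what a pooled Day-28 difference means, and they do not fill the Kaplan-Meier gap.

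**Conclusion.** The concern holds as a matter of interpretation and precision for one estimation-only secondary endpoint. Eligibility admits patients who already meet the Section 2 definition of respiratory failure; the pooled Day-28 proportion mixes two meanings of success; and the Kaplan-Meier display lacks a time-zero rule.

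The gain in precision is modest. It is about 20% of the variance, or 21 to 19 points of half-width, at a 30% entry share with 90% vs 50% success. With 90% vs 70% it is about 6%. The entry share and all Day-28 rates are assumptions.

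A reader might also infer that a treatment difference could come wholly from patients already in failure. The documents give nothing to support that. On the rates assumed in step 5 such patients supply part of the difference, 18% to 67% for entry shares of 10% to 50%.

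**What to change.** In Section 10.3:

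1. Define baseline respiratory failure as ordinal category 4 at the latest available assessment before dosing, following the Section 10.2 baseline definition. Do not simply take the Day-0 score: the infusion is also on Day 0, and Table 7-1 does not say which comes first. Patients randomized but never dosed stay in the intention-to-treat set, so state which value serves for them, for example the last one before randomization.
2. Give the overall Day-28 estimate as a Mantel-Haenszel risk difference across the two baseline strata, with its 95% confidence interval.
3. Tabulate the endpoint by stratum and arm, labelled descriptive, because a stratum may hold only a few patients or failures per arm.
4. State the event that the Kaplan-Meier display counts and how it treats patients in failure at entry, for example by showing it by baseline stratum.

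Leave eligibility and the intention-to-treat set unchanged.

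The cost is a few lines of analysis text, one table and possibly split curves, using data already collected. The drawback is that stratum results will be too imprecise to support separate conclusions. The text should be settled before unblinding, so that the breakdown is not a post-hoc choice.
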